Study participants who complete all baseline assessments will then be randomly assigned to eight group sessions of one of three manualized treatments: (1) pain education (ED), (2) self-hypnosis training (HYP), or (3) mindfulness meditation training (MM). Inclusion of the face-valid pain education condition will allow us to control for many of the non-specific effects of HYP and MM treatments, including time, therapist attention, and treatment outcome expectancy.^{52, 53} Moreover, this condition is expected to be beneficial in ways that are not reflected in our outcome measures (e.g., improved knowledge/understanding of chronic pain, improved communication skills).

This RCT will examine the immediate post-treatment and long-term (3- and 6-months from end of treatment) efficacy and mechanisms of HYP and MM on average pain intensity (primary outcome), worst pain intensity, depression, anxiety, sleep disturbance, pain interference, medication use, post-traumatic stress, thoughts about pain, mindfulness and global satisfaction relative to the ED intervention designed to control for time, dose, attention, and other nonspecific therapeutic effects such as therapeutic alliance. Self-report data will be collected primarily via telephone excluding the cognitive assessment and hypnotic and relaxation exercise.

This RCT will also examine whether pain reduction with HYP and MM will be significantly associated with different patterns of baseline brain activity. Brain activity data will be collected

via electroencephalogram (EEG) once before and once after treatment to test the second aim of this study.

The study uses a 3-group parallel design. During their study participation, all participants will continue to receive their usual medical, psychiatric, and psychotherapeutic care. Participants will also be offered to participate in one or both treatments they did not receive following end of participation in the main phase.

Sub-Study:

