The research staff member, a UW IBIC employee with a Without Compensation (WOC) appointment at the VA, will obtain consent at the IBIC using the UW EEG consent document. They would then collect the EEG activity data, and ask the participant to remain as still as possible during portions of the assessment. The EEG technician will collect from the participant data regarding medication used within 24 hours of assessment. S/he will also ask the participant to rate the intensity of his or her pain just before the assessment (current pain), after a few minutes of the assessment (current pain and worst, least, and average pain over the past few minutes), and at the end of the EEG session (current pain, and worst, least, and average pain over the past few minutes), using 0-10 Numerical Rating Scales. Finally, the technician will ask the participant to think about their chronic pain in general or a particularly painful event for a period of two minutes. The technician will then ask the participant to rate his/her pain intensity, as well as answer some questions about how s/he thought about his/her pain during the two-minute period. The EEG technician then will ask each participant whether they experienced any negative effects they associate with study procedures to make certain all adverse events related to the study are recorded.

The entire brain wave activity assessment will take approximately 45-60 minutes to complete. Participants will be compensated \$100 for completion of the brain wave activity assessment via a check written from the Seattle Institute for Biomedical and Clinical Research (SIBCR). The check will be sent via USPS mail and accompanied by a payment cover letter.

The brain wave activity assessment must be administered at IBIC, and only after completion of the informed consent process. All other assessment activities may be administered at IBIC or a VA site. So, participants have some options around where they do their baseline assessments and in what combination.

Subjects will be asked to complete the same brain activity assessment following completion of treatment following the same procedures above.

The one difference will be, during the post-treatment assessment, participants will complete an additional 10-minute assessment portion in which they think about the skills they learned during the treatment sessions.

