Participants will report the skills s/he used during this assessment portion, as well as general experience during this portion. Participants will be compensated \$100 for completion of the brain wave activity assessment via a check written from the Seattle Institute for Biomedical and

Clinical Research (SIBCR). The check will be sent via USPS mail and accompanied by a payment cover letter.

Participants may still participate in the study if they decline to participate in the EEG assessments. The EEG assessment is optional.

D6k. Assessment: Pre-Treatment and General Overview

Subjective reports of pain intensity vary over time, and to most accurately measure pain intensity (our primary outcome), it is most valid to assess multiple times and take an average. Hence, we have developed a method of assessment that will seek to obtain up to four telephone assessments over a period of one week or 7 days. In addition, research staff will seek to administer these assessments ideally with a minimum of 24 hours between each assessment. Given scheduling conflicts, research staff may collect each assessment no less than 22 hours between each assessment if necessary.

During *each* telephone contact, research staff will ask participants, at minimum, to rate their current, average, worst and least pain intensity over the past 24 hours, as well as their average pain intensity over the past week.

In addition, if possible, research staff will ask the participant to rate their current, average, worst and least pain intensity over the past week during the final telephone contact. These assessments will be referred to as “short assessments.” The primary outcome will be an average of all of the 24-hour ratings (range=1-4 ratings) of average pain intensity obtained over a period of one week during each assessment period.

In addition, sometime during this assessment period researchers will ask questions regarding pain interference, depression, anxiety, sleep disturbance, post-traumatic stress disorder (PTSD) symptoms, medication use, medical services utilization, thoughts about pain and treatment motivation. This latter set of questions will only be asked once during the assessment period, and will be referred to as “the long assessment.”

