The goal of mediation analyses is to examine whether group assignment (determined by randomization at baseline) impacts the change in pain intensity (primary outcome) from baseline to post-treatment through indirect effects on the hypothesized mediators (measured midway

between baseline and post-treatment). Our potential mediators have been identified a priori and are shown in the table of measures (Table 4).

To evaluate the association between intervention type, potential mediating factors, and change in pain intensity, we will first run models with individual mediators to get unadjusted estimates and to estimate the degree of confounding in subsequent multivariate models. Per Hayes & Rockwood's 2017 recommendations, we will test multiple mediators in the same model, to more accurately reflect our theoretical understanding of parallel biological and psychological mediating processes, and to facilitate comparison of the size of indirect effects through different mediators. Mediators to be included in the model include change in EEG composite scores for theta, alpha, beta, and gamma bandwidths, pain acceptance, catastrophizing, mindfulness, therapeutic alliance, and skill practice. Also per the recommendations of Hayes and Rockwood (2017), we will compute bootstrap confidence intervals for the indirect effects. All mediation analyses will be done using PROCESS, a free downloadable add-on available for SPSS and SAS (the analysis packages we will use for the study's data analysis). PROCESS includes the computational code to generate a primary estimate for the mediation model which represents the indirect, or mediated effect, and allows for inclusion of moderator variables.

Our study is longitudinal and, in addition to posttreatment assessments, we have collected data at 3- and 6-months post-treatment on outcomes and all other variables (mediators and moderators). While the approach used in the PROCESS software can be somewhat adapted for longitudinal analysis, the most appropriate analysis would be longitudinal structural equations models, particularly latent growth models (e.g., Goldsmith et al. 2018). These models require specialized software such as AMOS or LISREL and are beyond the scope of our exploratory aims. If we are able to access such statistical resources in the future, however, we would like to leverage this dataset for these exploratory purposes.

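### The mediation model presumes mid-treatment mediators, but EEG is recorded only before and after treatment, so the direction between EEG change and pain change is not identified

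*Combined protocol and SAP*

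**What the plan says.** Section D6x, Mediation analyses, asks whether group assignment "impacts the change in pain intensity (primary outcome) from baseline to post-treatment". The route it proposes is "through indirect effects on the hypothesized mediators (measured midway", that is, part-way through the treatment period. It first fits each mediator alone. It then fits several mediators in parallel, so that the sizes of their indirect effects can be compared, with bootstrap confidence intervals from PROCESS. On the content of that model it says: "Mediators to be included in the model include change in EEG composite scores for theta, alpha, beta, and gamma bandwidths". Five further mediators enter alongside: skill practice, therapeutic alliance, mindfulness, catastrophizing and pain acceptance.

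On EEG timing, the Synopsis (D1) says brain activity is collected "via electroencephalogram (EEG) once before and once after treatment". D6j adds: "Subjects will be asked to complete the same brain activity assessment following completion of treatment following the same procedures above". It also says: "The EEG assessment is optional". Table 1, Table 5 and Appendix 1 agree that there are two recordings.

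A later paragraph of the mediation section says that data were also collected at 3 and 6 months "on outcomes and all other variables (mediators and moderators").

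**The concern.** A mediation model for a randomised trial needs two orderings: treatment before mediator, and mediator before outcome. Randomisation supplies the first. The plan relies on mid-course measurement for the second, and EEG has none. The only EEG change available runs from pre- to post-treatment, the same interval as the pain change it is meant to explain. No text places the second EEG before the post-treatment pain ratings.

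EEG change and pain change will then be correlated whether EEG change reduces pain, pain relief alters EEG, or something else moves both. The regression labels any such correlation an indirect effect through EEG if treatment also shifts EEG. The plan would give it a confidence interval and compare it with the effects of mediators that were measured during treatment. What is at stake is a mechanistic claim, in a trial whose stated purpose includes mechanisms.

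**Working it through.** **Timing, from D6k, Table 5 and Appendix 1.**

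| Assessment period | Pain | EEG | Pain acceptance, catastrophizing, mindfulness |
|---|---|---|---|
| Pre-treatment | yes | yes | yes |
| After sessions 2, 4 and 6 | yes | no | yes |
| Post-treatment (Weeks 11-12) | yes | yes | yes |
| 3 and 6 months | yes | no | yes |

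EEG is present at 2 of the 7 pain assessment periods and at 0 of the 3 mid-treatment periods. The mid-course definition cannot hold for it, and the statement about 3 and 6 months is untrue for it. Therapeutic alliance is a lesser case. Table 5 measures it during treatment only at two weeks, so it precedes the outcome but is not strictly midway, and the table shows no 3- or 6-month value.

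**Size of a false indirect effect.** The documents give no power, sample size or error rate for the mediation analysis, so there is no planned figure to reproduce. The following is an illustration.

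Inputs:
- n = 80 per arm, and SD of pain change 1, the largest value considered (D6z).
- Pain differences from education of 0.6 - 0.3 = 0.3, 0.8 - 0.3 = 0.5 and 1.0 - 0.3 = 0.7 (D6z).
- Assumed, not in the documents: within-arm EEG-pain correlation r of 0.1 to 0.5, one active arm against education, one mediator.

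Set-up with no mediation: pain change Y = dX + error with SD 1. EEG change M = rY + noise, scaled so that M has within-arm SD 1. Pain drives EEG, and EEG has no effect on pain.

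What the mediation regressions estimate:
- a path (treatment on EEG) = rd
- b path (EEG on pain, given treatment) = cov(M, Y | X) / var(M | X) = r
- false indirect effect = a × b = r²d, a share r² of the treatment effect: 1%, 9%, 16% and 25% for r = 0.1, 0.3, 0.4 and 0.5.

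Chance that both paths are significant at two-sided 0.05:
- z_a = rd / √(2/80) = rd / 0.158
- z_b = r / √((1 - r²)/160)
- for each path, P = Φ(z - 1.96) + Φ(-z - 1.96); multiply the two.

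Example, d = 0.5 and r = 0.3: z_a = 0.15/0.158 = 0.95, P = 15.8%. z_b = 0.3/0.0754 = 3.98, P = 97.8%. Product 15.4%.

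| Pain effect | r = 0.1 | r = 0.3 | r = 0.4 | r = 0.5 |
|---|---|---|---|---|
| 0.3 SD | 1.3% | 8.6% | 11.8% | 15.8% |
| 0.5 SD | 1.5% | 15.4% | 24.4% | 35.3% |
| 0.7 SD | 1.8% | 25.9% | 42.5% | 60.0% |

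Simulations of the same set-up agree to within about two points: 8-18%, 15-36% and 27-59% for r = 0.3-0.5. For the largest self-hypnosis assumption (1.4 - 0.3 = 1.1 SD), simulation with a confidence interval for a × b gave 52% at r = 0.3 and 93% at r = 0.5. With 50 per arm, an assumed figure because EEG is optional, the same method gave 10-26% at 0.5 SD and 14-42% at 0.7 SD for r = 0.3-0.5.

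**The case against.** **The plan already limits the claim.** Mediation is labelled exploratory, significant findings are said only to support more definitive testing, and D6x concedes that longitudinal structural equation models would suit better. This lowers the weight of the point. It does not supply a direction, and a structural equation model could not create the missing mid-treatment EEG.

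**The rates depend on an assumed correlation.** This stands. At 0.1 the problem is negligible. The illustration also has one mediator and two arms, against parallel mediators and three arms in the plan. A reader might infer that the model will report a false EEG effect. The documents support only that it can, and most settings in the table lie below 50%.

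**Midway timing does not settle direction for psychological mediators either.** This also stands, because pain is changing by sessions 2, 4 and 6. Simulating early pain relief that drives a mid-course mediator, with no true mediation and an assumed mid-to-post pain correlation of 0.5-0.7, gave false mediation in 7-10% of trials at 0.5 SD with a link of 0.3. With a link of 0.5 the rates were 31-35% at 0.5 SD and 53-58% at 0.7 SD. Mid-course measurement reduces the concern without removing it.

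**Two further inferences go too far.** One is that EEG mediation has no temporal order at all; randomisation precedes EEG change, so only the EEG-to-pain step is open. The other is that optional EEG will cut the sample for the psychological mediators. Single-mediator models are fitted first, and no complete-case rule is stated. The missing-data plan speaks of outcomes, so handling of missing mediators is unspecified rather than wrong.

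**Conclusion.** The concern holds as a contradiction within the current mediation section: a timing rule is stated for all mediators, and EEG cannot meet it. The conclusion that direction is unidentified rests on the schedules alone and needs no numerical assumption.

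The size does need assumptions. If pain relief drives EEG change, the false-mediation rate with 80 per arm runs from 1-2% at a correlation of 0.1 up to about 60% at 0.5 with a 0.7 SD pain effect. The falsely credited share of the treatment effect runs from 1% to 25%.

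The point should be addressed before the mediation results are reported, but its reach is limited. The primary analysis, the sample size and the Aim 2 hypothesis on baseline EEG as a moderator do not depend on it.

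**What to change.** 1. Limit the mid-course timing statement and the parallel-mediator model to mediators with during-treatment values, and name the assessment used for each. State that pain is also changing by then, so direction remains uncertain for these too.
2. Analyse EEG change in its own section. Report its relation to pain change over the same window as a concurrent association, not as an indirect effect, and do not rank it against the psychological mediators.
3. Correct the sentence saying that all mediators were collected at 3 and 6 months. It is untrue for EEG and, on Table 5, for therapeutic alliance.
4. Optionally, add a model of pre- to post-treatment EEG change on 3-month pain, adjusted for post-treatment pain, labelled as an analysis of further pain change after treatment. It is not a substitute. If EEG acts on pain during treatment and reaches 3-month pain only through post-treatment pain, the adjusted EEG coefficient is zero and so is the indirect effect. In simulations of full EEG mediation (80 per arm, assumed paths a = 0.5-1.0 and b = 0.5-0.7, pain correlation 0.7), this model found mediation in 4-6% of trials, against 87-100% for the concurrent model. Its merit is protection against reverse causation: false mediation fell to 1-3% in the settings tried, though measurement error in post-treatment pain could leave some bias.

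The cost is SAP wording, with no new data. The small loss is the direct comparison of EEG and psychological indirect effects in one model.

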As a secondary sleep outcome, for this aim we will add the PROMIS Sleep Disturbance Short Form, which is already being administered as a self-report measure of sleep quality within the parent project. This will allow us to evaluate the level of congruence between the parent grant and the subsample studied in the supplement.

For the statistical analyses in support of aim 2, we will determine whether changes in self-reported sleep quality and in actigraphic sleep duration in the hypnosis and mindfulness meditation treatment groups and the control group *precede* changes in pain, or vice versa, from pre-treatment to mid-treatment to immediate post-treatment to 3-month follow-up. Specifically, we will evaluate the association between early treatment changes in self-reported sleep quality (from pre-treatment to mid-treatment) and late treatment changes in pain (from mid-treatment to post-treatment), and vice versa.

We will also evaluate the association between treatment-related changes in objective sleep duration (from pre-treatment to post-treatment) and post-treatment changes in pain (from post-treatment to 3-month follow-up), and vice versa. *We hypothesize that changes in sleep quality and duration precede (and thus predict) subsequent changes in pain intensity.* Secondly, we will investigate whether associations are moderated by treatment group. *We hypothesize that larger lagged effects will occur for the two treatment conditions, relative to the control condition.* Our hypothesis testing for aim 2 will be based on cross-lagged regression analysis.^{103, 104}

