We will then apply an autoregressive cross-lagged model to investigate the cross-lagged relationship between actigraphically measured sleep duration and pain outcomes from the parent project. For each of the two intervention groups, we will use an autoregressive regression model on sleep duration with subjective pain as the covariate of interest, and our objective will be to test the regression coefficient for this covariate against zero (two-tailed). We will account for the variance in sleep duration at the post-intervention and follow-up time points that is explained by sleep duration at the respective immediately preceding time point, ρ^2 , where the estimated value for ρ is drawn from our previous data set described above ($\rho=0.122$). With 39 subjects, we will have 80% statistical power, at a type I error threshold of $\alpha=0.05$, to detect a cross-lagged relationship between sleep duration and subjective pain at the immediately preceding time point if this relationship explains at least 17.3% of the variance (nQuery 7.0, Elashoff, 2007).

HUMAN PARTICIPANTS SECTION

1. Risk to Participants

1a. Human Participants Involvement and Characteristics

We plan to enroll up to ~~343~~ 355 participants into the study. Male and female participants 18 years of age or older who have chronic pain will be approached to participate in the study. Participants will be recruited from clinics at the Seattle and American Lake Campuses of VAPSHCS, as well as community-based outpatient clinics (CBOC).

Veterans will be recruited from several clinics and service lines at VAPSHCS: the Rehabilitation Care Service (which includes the Polytrauma Network Site for the northwest four

states, the Multiple Sclerosis Clinic/Center of Excellence, Prosthetic/Limb Loss Clinic, and Musculoskeletal Clinic), and the Spinal Cord Injury Service. Each of these clinics sees 200-500 new Veteran patients per year and carries an ongoing patient load of 200 – 400 patients. We will also recruit patients from Primary Care as needed, which carries an ongoing patient load of 19,000 patients per year.

Participants will also be recruited from VA community-based outpatient clinics (CBOC).

1b. Sources of Materials

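### Sleep sub-study Aim 2: the lag tests pair a sleep change and a pain change that share a visit, and no prior-pain term is written for the sleep-to-pain path, so the test as worded is biased against Hypothesis 2

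*Combined protocol and SAP*

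**What the plan says.** Section D6x (Statistical Analyses, Sub-Study, aim 2) defines two lag tests.

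- Sleep quality: "the association between early treatment changes in self-reported sleep quality (from pre-treatment to mid-treatment) and late treatment changes in pain", where the pain change runs from mid- to post-treatment. The reverse is also planned, since the sentence ends "late treatment changes in pain (from mid-treatment to post-treatment), and vice versa".
- Actigraphy: "the association between treatment-related changes in objective sleep duration (from pre-treatment to post-treatment) and post-treatment changes in pain", where the pain change runs from post-treatment to 3 months. The reverse is planned here too.

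The hypothesis is directional in time: "We hypothesize that changes in sleep quality and duration precede (and thus predict) subsequent changes in pain intensity". The method is then named: "Our hypothesis testing for aim 2 will be based on cross-lagged regression analysis". No covariates are listed.

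The sub-study power section (under D6z) adds two models, each for one intervention group with 39 subjects. The first regresses pain on sleep duration and has no prior-pain term. The second is autoregressive, with sleep duration as the outcome and pain as the covariate: "We will account for the variance in sleep duration at the post-intervention and follow-up time points" that preceding sleep duration explains. This is the pain-to-sleep direction, in levels.

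Section D1 aligns sleep collection with the parent trial's assessment points. Section D6k makes the pain score an average of 24-hour ratings within one week at each point.

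**The concern.** In the first test the predictor contains plus the mid-visit sleep score and the outcome contains minus the mid-visit pain score. If people report less pain in the weeks they sleep better, the two changes are correlated even when sleep has no effect on later pain. Someone with an unusually good mid-treatment week shows an early sleep gain and low mid-visit pain, and then an apparent later rise in pain.

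The sign is opposite to Hypothesis 2. Coding sleep as disturbance makes no difference, because the expected sign flips as well. A real lag can therefore be diluted or cancelled, or a significant lag reported in the wrong direction. Section J says that evidence that a focus on sleep improves pain would support later trials of sleep interventions, so the sleep-to-pain estimate is what readers will use.

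**Working it through.** **The plan's own figures.** For one added covariate, the noncentrality is n × R² / (1 − R² − R²prior), with n = 39 and two-sided α = 0.05.
- Simple regression: 39 × 0.175 / 0.825 = 8.27, power 0.800.
- Autoregressive: R²prior = 0.122² = 0.0149, so 39 × 0.173 / 0.8121 = 8.31, power 0.801.

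Both stated detectable variances (17.5% and 17.3%) reproduce. Neither allows for the shared visit.

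**Algebra.** Let visits 1, 2 and 3 be pre, mid and post. Write S_t = a + s_t and P_t = b + p_t, with stable person parts a and b (covariance κ), same-visit state covariance c = r·σ_s·σ_p, no lag and no carry-over. Then

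Cov(S2 − S1, P3 − P2) = Cov(S2,P3) − Cov(S2,P2) − Cov(S1,P3) + Cov(S1,P2) = κ − (κ + c) − κ + κ = −c.

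The change variances are 2σ_s² and 2σ_p², so the correlation is **−r/2**. If states follow AR(1) with common persistence φ, it is −r(1 − φ)/2.

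**Size.** r is not in the documents; −0.2 to −0.4 is an assumed range. Rejection rates are from simulation with half the variance stable, no lag and φ = 0.

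| Same-visit r | Spurious correlation | Rejection, n = 39 | Rejection, n = 117 |
|---|---|---|---|
| −0.2 | +0.10 | 9% | 19% |
| −0.3 | +0.15 | 15% | 36–37% |
| −0.4 | +0.20 | 23% | 58–60% |

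Nearly all rejections fall in the direction opposite to Hypothesis 2.

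**Persistence.** At r = −0.4 and n = 117, the correlation is 0.4 × 0.5 / 2 = 0.10 for φ = 0.5 (about 19% rejection) and 0.4 × 0.3 / 2 = 0.06 for φ = 0.7 (about 10%). At r = −0.3 and n = 39, rejection is about 7% and 6%.

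**Adjusting for shared-visit pain only.** The residual P3 − βP2 has covariance −βc with S2 − S1, and β is above zero whenever people differ stably in pain. Rejection remains 6–11% at n = 39 and 9–25% at n = 117.

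**Adjusting for pain at both earlier visits.** Under the no-carry-over model P1 and P2 get equal coefficients β. The covariance of P3 − β(P1 + P2) with S2 − S1 is then 0 − β(c − c) = 0. Simulated rejection is about 5% at both sample sizes.

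**Unequal persistence.** With sleep and pain at 0.2 and 0.6, either way round, the two-covariate model leaves about 6%. A rerun holding r at −0.4 at every visit gave 5% to 8% at n = 117. Holding only the early pain change constant is more exposed: 6% to 16% at n = 117 and r = −0.4 in the cases tried.

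**With a real lag** (pain falls 0.3 SD per SD of earlier sleep, n = 117), power in the right direction drops from 88% at r = 0 to 19% at r = −0.4 for change on change. With the early pain change held constant it is 77–78% in both cases.

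**The case against.** The strongest reply is that D6x only describes which intervals are compared and then names cross-lagged regression, a method that usually carries the earlier outcome. D6z also calls its model autoregressive. On that view the plan is incompletely written, not wrong. In part this stands: a reader might infer that the plan commits to an unadjusted correlation of change scores, and the documents do not go that far. But no section gives a prior-pain term for the sleep-to-pain path, so an analyst could follow D6x to the letter and obtain the biased estimate.

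A second reply is that the ordinary level model (later pain on preceding pain and preceding sleep) avoids the problem. With person-level r of −0.3 and same-visit r of −0.2, −0.3 and −0.4, it rejects 5.5%, 4.5% and 7.1% of the time at n = 117, and about 5% at n = 39. That rests on the two correlations being similar. When they differ (for example 0 against −0.4, or −0.6 against −0.2), rejection at n = 117 is 24–28%, and the bias can run either way.

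Three further limits stand.
- The size depends on an r and a carry-over that the documents do not give. Nothing shows that actigraphic duration has the same r with pain as self-reported sleep quality.
- The planned regressions are per group, so n = 39 is the relevant column; n = 117 assumes pooling.
- A reader might infer that the which-comes-first question cannot be answered at all. That is too strong. With equal persistence the reverse path carries a bias of the same size, so comparing directions is less distorted than either test alone. The arm-moderation test is unaffected on average if r is equal across arms. Nor would the artefact falsely confirm Hypothesis 2 on the sleep-to-pain path, because it runs against it.

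**Conclusion.** The concern holds as a conditional one. Both Aim 2 lag tests are worded as associations between changes that share a visit, and no written model holds prior pain constant in the direction that Hypothesis 2 claims. If run as worded, same-visit correlation biases that lag against the hypothesis by up to half its own size. Under the assumed r of −0.2 to −0.4 with no carry-over, the 5% test becomes roughly a 9–23% test at 39 per group. Moderate or strong persistence brings it much closer to nominal. The choice of covariates matters: shared-visit pain alone is not enough, and a level-only model is sound only under a condition the plan cannot check in advance. This deserves correction before analysis. It does not touch the main trial or sub-study Aim 1.

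**What to change.** In D6x, replace the two change-on-change associations with written models:

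- post-treatment pain on the pre-to-mid sleep-quality change, mid pain and pre pain;
- 3-month pain on the pre-to-post sleep-duration change, post pain and pre pain;
- for each reverse path, the mirror model: later sleep on the early pain change, with both preceding sleep values as covariates.

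Align the D6z models with these, state whether they are fitted per group or pooled, and restate the 17.5% and 17.3% detectable variances accordingly.

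The cost is wording plus one or two degrees of freedom per model: at n = 39, residual degrees of freedom go from 37 to 35 relative to the simple association. No new data are needed, since every value comes from visits that the lag already uses. There is some loss of power if same-visit correlation is in fact zero: in the real-lag example above, 88% falls to 77% when the early pain change is held constant. That buys an estimate whose sign does not depend on an unknown same-visit correlation under the equal-persistence models tried. Strongly unequal persistence would leave a small residual bias, which the report should mention.
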